10.0	STATISTICAL CONSIDERATIONS	31
10.1	Study Design/Study Endpoints	31
10.2	Sample Size and Accrual	31
10.3	Data Analyses Plans	31
11.0	STUDY MANAGEMENT	33
11.1	Institutional Review Board (IRB) Approval and Consent	33
11.2	Amendments	33
11.3	Registration Procedures	33
11.4	Data Management and Monitoring/Auditing	34
11.5	Adherence to the Protocol	34
11.6	Investigator Obligations	35

11.7 Publication Policy	35
REFERENCES	36
APPENDICES.....	41

LIST OF ABBREVIATIONS

Abbreviation	Meaning
AE	Adverse Event
AVO	Acidic Vesicular Organelles
CD	Cytosine Deaminase
CE	Carboxylesterase
CR	Complete Response
CRAd	Conditionally replicative Adenovirus
CRAd-S-pk7	CrAd-Survivin-pk7
DLT	Dose Limiting Toxicity
DMC	Data Monitoring Committee
FDA	Food and Drug Administration
GBM	Glioblastoma
GFAP	Glial fibrillary acidic protein
GTR	Gross total resection
hTR	Human telomerase RNA
hTERT	Human telomerase reverse transcriptase
ICP	Increased intracranial pressure
KPS	Karnofsky Performance Status
LC3	Light-chain 3
MR	Minor Response
MRI	Magnetic Resonance Imaging
MSC	Mesenchymal Stem Cell
MTD	Maximum Tolerated Dose
NSC	Neural Stem Cell
OS	Overall Survival
OV	Oncolytic Virus
P	Progression
PFS	Progression Free Survival
PFU	Plaque Forming Units
PR	Partial Remission
PRb	Retinoblastoma protein
RT	Radiotherapy
TMZ	Temozolomide
TRAIL	Tumor necrosis factor–related apoptosis-inducing ligand
TSP	Tumor Specific Promoters
VP	Viral Particle

STUDY SCHEMA

Sample Schedule

Week 1	
Day 0	Intratumoral injection of NSC-CRAd-S-pk7
Days 6-7 (\pm 3 days)	Simulation for RT
Week 2-7	
Days 1-7 (\pm 3 days)	RT (Days 1-5 only) TMZ (75 mg/m ²)
Week 12	
5 Days on/23 Days off	TMZ (150-200 mg/m ²)

STUDY SUMMARY

Protocol Title:
A Phase I study of neural stem cell based virotherapy in combination with standard radiation and chemotherapy for patients with malignant glioma
Brief Protocol Title for the Lay Public (if applicable):
Viral stem cell based therapy for malignant glioma
Study Phase:
Phase I
Participating Sites:
Northwestern University
Rationale for this Study:
Malignant gliomas have a very poor prognosis with median survival measured in months rather than years. It is a disease in great need of novel therapeutic approaches. Based on the encouraging results of our preclinical studies described below, which demonstrate improved efficacy without added toxicity, the paradigm of NSC-CRAd-S-pk7 in combination with radiation and chemotherapy is well-suited for evaluation in malignant gliomas. The standard-of-care allows application of virotherapy as neoadjuvant therapy and assessment of the cooperative effects with radiation/chemotherapy without altering the standard treatment.
Objectives:
The primary objectives are to evaluate the safety of the combined therapy and determine the dose-limiting toxicity and maximum tolerated dose (MTD) for a future Phase II study. Secondary objectives are assessment of tumor response, overall survival, progression-free survival, overall survival and quality of life. An exploratory objective will be to evaluate cytokine profile and blood immune response to NSC-CRAd-S-pk7 and to determine whether survival rate correlates with extent of immune response.
Study Design:
Open label, Phase I, dose-escalation gene therapy clinical trial with two arms: Arm A – Unresectable disease, receive stereotactic intratumoral injection of NSC-CRAd-S-pk7 immediately following stereotactic biopsy confirmation of clinical diagnosis Arm B – Resectable or partially resectable, receive injection of NSC-CRAd-S-pk7 into remaining tumor or tumor bed after resection. Dose escalation will be performed independently for each arm and 3-6 patients will be enrolled per dose in each arm. Standard radiotherapy and chemotherapy will begin after NSC-CRAd-S-pk7 injection.
Endpoints:
The primary endpoint of this dose-escalation study is to determine the maximum tolerated dose (MTD) of NSC-CRAd-S-pk7 when administered with standard radiation and chemotherapy in patients with malignant glioma. The secondary endpoints include objective tumor response, overall survival, progression-free survival and quality of life. The exploratory endpoints include cytokine profile and blood immune response and their correlation with overall survival. In addition, RCR testing will be performed to determine long-term gene expression, and if present, correlation with overall survival.
Sample Size:

If all three dose levels are administered, the minimum number of patients enrolled will be 9 per arm and the maximum number of patients will be 18 per arm.

Estimated Duration of the Study

Based on projections from current clinical practice, it is anticipated that the accrual will take 12-18 months to complete.

Summary of Subject Eligibility Criteria:

Inclusion Criteria

- Patients must have presumed malignant glioma based on clinical and radiologic evaluation (pathologic confirmation of malignant glioma must be made at the time of stereotactic biopsy or resection prior to NSC-CRAd-S-pk7 injection; if this is not possible, the injection will not be performed and the subject will no longer be eligible for the study).
- Tumor must be accessible for injection and must not be located in the brainstem, or contained within the ventricular system.
- Planning to undergo standard radiation/chemotherapy
- 18 years of age or older.
- Performance status must be KPS \geq 70
- SGOT (AST) $<$ 3x upper limit of normal
- Serum creatinine $<$ 2mg/dl
- Platelets $>$ 100,000/mm³ and WBC $>$ 3000/mm³

Exclusion Criteria

- Prior or ongoing liver disease including known cirrhosis, hepatitis B or C infection but not to exclude patients with a distant history of resolved hepatitis A infection.
- Immunosuppressive drugs (with exception of corticosteroid).
- Known HIV+ patients.
- Acute infections (viral, bacterial or fungal infections requiring therapy).
- Pregnant or breast-feeding patients.
- Evidence of metastatic disease or other malignancy (except squamous or basal cell skin cancers).
- Prior radiation therapy to the brain or prior treatment for brain tumor
- Other serious co-morbid illness or compromised organ function.

Investigational Product Dosage and Administration:

Table 1 – Dose Escalation Schema

Cohort	Number NSCs Injected	Total Viral Dose Viral particles (vp)/patient
1	50 million (5×10^7)	6.25×10^{10}
2	100 million (1×10^8)	1.25×10^{11}
3	150 million (1.5×10^8)	1.875×10^{11}

Clinical Observations and Tests to be Performed:

- On day 0, stereotactic biopsy or resection of the tumor
- History and physical will be performed weekly, 2-4 weeks after completion of radiation and at least every 3 months for the first year.
- Quality of life questionnaire (FACT-Br version 4) once during week 2-3, 2-4 weeks after completion of radiation and every 3 months for the first year or until disease progression.
- CBC, platelets, creatinine, AST, ALT, and bilirubin will be monitored bi-weekly during administration (weeks 2, 4, and 6).
- Blood for immune research studies* (10 to 40 cc) may be collected in week 2-3 after the NSC-CRAd injection and 2-4 weeks after completion of radiation therapy
- MRI of the brain approximately 28 days after study product injection, 2-4 weeks after completion of radiation, and then every 2-3 months for the first year or until disease progression.
- If surgery is performed, tumor samples will be examined in conjunction with the pathologist and samples retained for future studies if consent given by the patient.
- Evaluation once a year for 5 years. Evaluations will include: Physical and neurological examination, MRI, and CBC with differential count.

Statistical Considerations:

Statistical analysis will be descriptive only, with no hypothesis testing. All the endpoint data will be collected and described in summary tables for both two arms at each dose. In general, descriptive statistics (n, mean, standard deviation, median, minimum, and maximum) will be presented for continuous variables. Frequencies and percentages will be calculated for categorical and ordinal variables at each category. All study data will be presented in by-subject data listings. Statistical analyses will be performed using SAS9.4 (SAS Institute Inc., Cary, NC).

The maximum tolerated dose (MTD) will be determined according to the dose escalation algorithm. If >2 patients do not complete the initial RT/TMZ phase or rule if > 2 patients experience life threatening or fatal neurologic toxicity, the trial will be stopped to analyze, in conjunction with the DMC, whether this regimen is tolerable.

Demographic (age, sex, height and weight) and baseline disease characteristics (including baseline KPS), will be summarized for both arms as well as the entire group. Kaplan-Meier curves and median survival estimates with confidence limits will be given for both overall survival and progression-free survival. The association of extent of immune response with overall survival will be determined by Cox's proportional hazards model.

Safety parameters will be analyzed descriptively, and presented in standard frequency tables (adverse events), shift tables (Laboratory parameters) and summaries of change from baseline over time (vital signs, physical examination, ECG and laboratory parameters).

Sponsor/Licensee:

Northwestern University/[name]

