Temozolomide (TMZ), an oral alkylating agent, was approved for refractory anaplastic astrocytoma in the United States and also for GBM in Europe. The drug has been shown to be modestly active as single agent in glioblastoma and moderately active against anaplastic astrocytoma (Yung et al, 1999). Up front therapy of malignant gliomas with TMZ concomitant with radiation followed by adjuvant TMZ was shown to be well tolerated with the most significant toxicity being grade 3-4 neutropenia and thrombocytopenia in less than 10% of patients (Stupp et al, 2002). In the last decade, TMZ was approved for use with radiation based on results of a randomized Phase III trial comparing this regimen to radiation alone which demonstrated a significant improvement in median survival from 12 to 15 months (Stupp et al, 2005).

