4.6.2 Radiation Therapy

Radiation will be determined and administered as per standard of care for the patient. It will start 10-14 days after NSC-CRAd-S-pk7 injection. It will consist of standard external field radiation, limited to the area of tumor and brain adjacent to tumor, fractionated at doses of 200 cGy per day for approximately six weeks to a total of 5500-6000 cGy.

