8.1.10 Side effects

- The most common adverse reactions ($\geq 10\%$ incidence) are: alopecia, fatigue, nausea, vomiting, headache, constipation, anorexia, convulsions, rash, hemiparesis, diarrhea, asthenia, fever, dizziness, coordination abnormal, viral infection, amnesia, and insomnia.
- The most common Grade 3 to 4 hematologic laboratory abnormalities ($\geq 10\%$ incidence) that have developed during treatment with temozolomide are: lymphopenia, thrombocytopenia, neutropenia, and leukopenia. Allergic reactions have also been reported.
- Less likely but severe adverse reactions include myelodysplastic syndrome and hepatotoxicity

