10.3.3 Safety Analyses

Safety endpoints include adverse events (including serious adverse events), deaths, laboratory parameters, vital signs, physical examination and ECG.

All Adverse event will be coded by System Organ Class (SOC) and Preferred Term using Medical Dictionary for Regulatory Activities (MedDRA) dictionary, and will be presented in frequency tables (overall and by intensity [CTCAE grading]) by SOC. In tables showing the overall incidence of adverse events, subjects who experienced the same event on more than one occasion are counted only once in the calculation of the event frequency. Listings will be presented by subject for all adverse events as well as for serious adverse events, adverse events associated with death, and adverse events leading to discontinuation from the study, unanticipated problems involving risks to subject or others. The following information will be included: start date, stop date, severity, relationship, outcome, and duration. Deaths will be listed and summarized descriptively.

Laboratory data will be presented as summary statistics by dose group using both shift and frequency tables. For each continuous laboratory parameter, results will be categorized as low, normal or high based on the laboratory normal ranges. Subjects who had a shift to low and those who had a shift to high from baseline to any post-dosing assessment will be summarized. All out-of-range and clinically significant laboratory results will be identified in subject data listings.

Individual patient values of vital sign parameters including systolic and diastolic blood pressure and heart rate will be listed by patient. The absolute and percentage changes from baseline will be computed and potentially serious changes will be flagged. Appropriate summary statistics will be provided for all vital sign parameters.

The number and percentages of subjects in each dose group with normal and abnormal ECG performance status and physical examination results will be presented for evaluations at baseline and final visit. For each body system, changes in subjects' findings from baseline to final visit (no change, normal to abnormal, or abnormal to normal) will be tabulated for each dose group.

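### The AE frequency tables and the laboratory shift rule pool the 10-14 days before RT/TMZ with the RT/TMZ period, and no AE table is split by relationship to the product

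*Combined protocol and SAP*

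**What the plan says.** The synopsis (Statistical Considerations) makes safety analysis descriptive: "Safety parameters will be analyzed descriptively, and presented in standard frequency tables (adverse events), shift tables (Laboratory parameters". The same sentence goes on to promise "summaries of change from baseline over time (vital signs, physical examination, ECG and laboratory parameters".

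Section 10.3.3 gives the detail.
- **Adverse events** "will be presented in frequency tables (overall and by intensity [CTCAE grading]) by SOC", with each subject counted once per event. Start date and relationship are recorded, but the section uses them only in by-subject listings.
- **Laboratory data:** "Laboratory data will be presented as summary statistics by dose group using both shift and frequency tables". Values are classed as low, normal or high against laboratory ranges, and "Subjects who had a shift to low and those who had a shift to high from baseline to any post-dosing assessment will be summarized".

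On timing, Section 4.6.2 says of radiotherapy: "It will start 10-14 days after NSC-CRAd-S-pk7 injection". Section 4.1 gives the same interval for chemotherapy. Section 7.1 runs routine AE reporting through Day 56.

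On background toxicity, Section 1.1 reports "grade 3-4 neutropenia and thrombocytopenia in less than 10% of patients" for up-front radiation with temozolomide followed by adjuvant temozolomide. The temozolomide side-effect list (headed 8.1.10, under 8.2) begins "The most common Grade 3 to 4 hematologic laboratory abnormalities" and names lymphopenia, thrombocytopenia, neutropenia and leukopenia, at an incidence of 10% or more.

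**The concern.** Between injection and the first RT/TMZ dose a patient has had surgery and the product, and nothing else from the regimen. It is the only post-injection period in which RT/TMZ toxicity is impossible, and there is no control arm to supply that contrast another way. Both planned tables run straight across its end. An AE on Day 5 and one on Day 40 fall in the same cell, and a shift counts whenever it occurs after dosing.

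What differs between dose cohorts is the product; RT/TMZ is the same standard background throughout. With 3-6 patients per dose per arm, one or two temozolomide events falling unevenly across cohorts could look like a product dose trend in a hematologic row, or mask one. The AE tables offer no column that lets a reader check.

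**Working it through.** **1. The plan's own design figure.** Table 10 is the only computable one. For a true DLT rate p, the chance of escalating is (1-p)^3 + 3p(1-p)^2 × (1-p)^3. At p = 20, 30, 40, 50 and 60% this gives 70.9, 49.4, 30.9, 17.2 and 8.2%, against the stated 71, 49, 31, 17 and 8%. It reproduces. It takes no input from the AE or shift tables, so this point leaves it untouched.

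**2. How much of the AE window lies before RT/TMZ.** Routine AE reporting after injection covers Day 0 to Day 56. With RT/TMZ starting on Day 10 the earlier part is 10/56 = 18%; starting on Day 14 it is 14/56 = 25%. So 75-82% of the pooled window follows RT/TMZ start.

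**3. The background rate.** The documents do not settle it: Section 1.1 gives under 10% for two event types, and the temozolomide list gives 10% or more for four. I take b = 10% of patients as the central assumption and show 5-30% as a range. The 20% and 30% rows are assumptions only.

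**4. Chance of background events in a cohort.** With n patients and no product effect, the expected number affected is n × b and the chance of at least one is 1 - (1-b)^n. At b = 10%: 1 - 0.9^3 = 27% and 1 - 0.9^6 = 47%.

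**5. Chance of a spurious difference between two cohorts.** Let X1 and X2 be independent Binomial(n, b), and take P(|X1 - X2| ≥ 2).
- n = 3, b = 10%: the probabilities of 0, 1, 2 and 3 affected are 0.729, 0.243, 0.027 and 0.001. The sum is 2 × (0.729 × 0.027 + 0.729 × 0.001 + 0.243 × 0.001) = 0.041.
- n = 6, b = 10%: the two counts are equal with probability 0.418 and differ by exactly one with probability 0.449, leaving 1 - 0.418 - 0.449 = 0.133.

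| Assumed b | Expected, n = 3 / 6 | At least one, n = 3 / 6 | Differ by ≥ 2, 3 v 3 / 6 v 6 |
|---|---|---|---|
| 5% | 0.15 / 0.3 | 14% / 26% | 1% / 5% |
| 10% | 0.3 / 0.6 | 27% / 47% | 4% / 13% |
| 20% | 0.6 / 1.2 | 49% / 74% | 11% / 27% |
| 30% | 0.9 / 1.8 | 66% / 88% | 17% / 34% |

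Before RT/TMZ starts, the RT/TMZ contribution is zero at every b.

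**6. What this does not measure.** The table concerns patients with a grade 3-4 hematologic event. The shift tables use low/normal/high, not CTCAE grade, so these figures do not size the laboratory half. There the point rests on the wording of the shift rule alone.

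**The case against.** The case for leaving the tables alone has real substance.

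- **The pooled table answers the stated question.** Section 2.1 makes safety of the combined therapy a primary objective. This stands, and is why the overall tables should stay.
- **The information is not lost.** Listings carry start date and relationship for at most 36 patients, the synopsis promises laboratory change over time, and Section 4.2.1 sets a safety analysis 14 days after the first and second subjects are treated, close to the pre-RT/TMZ period. This stands too. A reader might infer that the product's contribution cannot be read at all; the documents do not support that. What is missing is AE incidence and shifts by period in the summary tables. Rebuilding them from listings leaves the cut point to be chosen after the data are seen.
- **The background is modest.** A reader might infer that temozolomide toxicity fills the tables. At 10%, a cohort of 6 expects 0.6 affected patients and has a 53% chance of none. Rows are by SOC, so hematologic events do not obscure nervous-system rows. Section 1.1's rate also includes adjuvant temozolomide, which Table 3 places at week 12, after routine AE reporting ends.
- **A split cannot isolate the product.** Surgery shares the first period. Section 1.3.4 reports a preclinical 100-fold rise in viral replication with radiation, so product effects may emerge during RT/TMZ. Both limits stand. The split shows a period free of RT/TMZ toxicity and nothing more.
- **A fuller SAP is promised.** Section 10.3 defers detail to a plan due before database lock. That is a suitable home for the change, but nothing in the current text commits to it.

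**Conclusion.** The point holds as a reporting gap that is cheap to close. As written, Section 10.3.3 merges two periods with different exposures and gives no AE table by relationship, so temozolomide's hematologic toxicity and any product effect share the same rows.

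At an assumed 10% background rate, a cohort shows at least one background patient with probability 27% (n = 3) to 47% (n = 6), and two cohorts differ by two or more with probability 4% to 13% when the product does nothing. These figures assume independent patients, equal cohort sizes and one common background rate. They move with that rate, which the documents leave unsettled.

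A reader might go further and infer that these tables drive the Phase II dose. They do not: Sections 4.2, 10.2 and 10.3.2.2 derive it from the 3+3 rules applied to DLTs, and no AE or shift table enters that decision. The consequence is limited to how the safety results can be interpreted.

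**What to change.** In Section 10.3.3, with a matching line in the synopsis and in the later SAP:

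1. Keep the overall AE tables as planned.
2. Add AE columns by onset period, by arm and dose: from injection to the day before the patient's first RT/TMZ dose, and from that dose onward. Use the actual start date, because the Day 14 visit can fall on or after it.
3. Add a column for events rated at least possibly related to the product.
4. Report laboratory shifts from baseline to worst value separately before and after RT/TMZ start.

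The cost is wording and extra columns. AE start dates and attribution are already planned in the listings, and the laboratory split needs only assessment dates and the first RT/TMZ date. The downsides should be stated with the tables: counts per column will be small, surgical effects share the first period, and product effects that emerge during RT/TMZ cannot be separated without a control. Fixing the cut point before database lock keeps it prespecified.

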1.0 INTRODUCTION – BACKGROUND & RATIONALE

1.1 Disease Background

Brain tumors are a relatively common malignancy for which standard treatments do not provide satisfactory median or long-term results. There are an estimated 17,000 new cases and 13,100 deaths from primary nervous system tumors in 2007, the majority of which are malignant gliomas (American Cancer Society). Slower growing, less aggressive gliomas are referred to as low grade or benign, whereas higher grade, malignant gliomas include malignant astrocytomas (36% of gliomas) and glioblastoma multiforme (GBM; 47% of gliomas and 21.7% of all primary brain tumors) (Levin et al, 2001). Therapy, including surgery, radiation and chemotherapy, is essentially palliative. Although neoplasms located within the frontal, temporal or occipital poles of the brain are amenable to “gross total resection” (GTR), these operations provide little control to the microscopic foci of tumor outside the main mass. Many malignant gliomas located within the corpus callosum, basal ganglia, brainstem and areas of eloquent cortex (speech, motor or visual

areas) are not resectable. For both GTR and non-resectable masses, radiation therapy is the major therapy provided after diagnosis. Its efficacy is limited by the low radiation sensitivity of tumor cells and the inclusion of normal brain tissue within radiation fields (Levin et al, 2001). With conventional radiation therapy, the median survival time for patients with anaplastic astrocytoma is 36 months, and the 3-year survival rate is approximately 55%. (Prados et al, 1999). In contrast, the median survival time for patients with GBM is 10 months and the 3-year survival rate is only 6% (Leibel et al, 1994).

Temozolomide (TMZ), an oral alkylating agent, was approved for refractory anaplastic astrocytoma in the United States and also for GBM in Europe. The drug has been shown to be modestly active as single agent in glioblastoma and moderately active against anaplastic astrocytoma (Yung et al, 1999). Up front therapy of malignant gliomas with TMZ concomitant with radiation followed by adjuvant TMZ was shown to be well tolerated with the most significant toxicity being grade 3-4 neutropenia and thrombocytopenia in less than 10% of patients (Stupp et al, 2002). In the last decade, TMZ was approved for use with radiation based on results of a randomized Phase III trial comparing this regimen to radiation alone which demonstrated a significant improvement in median survival from 12 to 15 months (Stupp et al, 2005).

